3.1 Clinical Investigation Procedures and Follow-up Schedule

A total of up to 107 subjects will be registered in the SPIRIT 48 study. Subjects registered in the study must have exactly one single *de novo* native coronary target lesion (defined in **Section 5.3**), which is eligible to be treated by a single ABT NG DES 48. Planned overlap is not allowed for the treatment of target lesion. If a bailout stent is necessary for the target lesion, a XIENCE family stent with appropriate size (including the ABT NG DES 48) must be used. A non-target lesion, if is located in a different epicardial coronary vessel than the target lesion, is allowed to be treated by stents other than the ABT NG DES 48 per site's standard of care during index procedure. All subjects must be treated with only one ABT NG DES 48.

- Lesions and stent usage: up to two treated lesions, must have exactly one long lesion that is treated by one ABT NG DES 48
 - Single lesion: one *de novo* native coronary artery long lesion (> 32 mm and ≤ 44 mm) as the target lesion, that must be treated a single ABT NG DES 48
 - Two lesions: one target lesion and one non-target lesion, each in different epicardial coronary vessels:
 - Target Lesion: one *de novo* native coronary artery long lesion (> 32 mm and ≤ 44 mm), that must be treated with a single ABT NG DES 48
 - Non-target lesion: one *de novo* native coronary artery lesion, that must be treated by stents other than the ABT NG DES 48 per site's standard of care

A maximum of 40% of subjects with two treated lesions can be registered in the study. At least 50% of the subjects will be registered at US sites.

Each subject will be followed for a two-year period. All subjects will have a hospital or office follow-up visit at 30 days, 6 months, 1 year and 2 years. An office visit is required for 1-year follow-up. All follow-ups must be conducted directly with the subject. Refer to detailed follow-up schedule in **Section 6.5.4**.

Note: If the scheduled visit occurs outside of the allowed window, it is not considered a missed visit/contact. It is a protocol deviation but still considered a completed visit.

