3.2.2 Angiographic Core lab

All angiographic data of this clinical investigation will be assessed by the Angiographic Core Lab. The Angiographic Core Lab will determine the type of revascularization (i.e., TLR, TVR or non-TVR), stent thrombosis, or necessary assessments. Angiography must be performed per the angiographic core laboratory guidelines. Angiographic data includes:

- Pre-procedure Morphology
- Pre-procedure quantitative coronary angiography (QCA)
- Post-procedure (Final) Morphology
- Post-procedure (Final) QCA
- Unscheduled visit Morphology and/or QCA

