6.5.1 Follow-up for All Subjects

Subjects registered in the clinical investigation will receive the following clinical follow-up:

- 1 month (30 ± 7 days): office visit/telephone contact (office visit is strongly recommended whenever possible)
- 6 months (180 ± 14 days): office visit/telephone contact (office visit is strongly recommended whenever possible)
- 12 months (365 ± 28 days): office visit (Note: a formal office visit is required at 12-month follow-up to ensure a thorough clinical evaluation. A telephone contact is an option *only* for subjects who would otherwise be lost to follow-up due to being unable to complete an office visit)
- 24 months (730 ± 28 days): office visit/telephone contact (office visit is strongly recommended whenever possible)

Clinical Investigation Plan

Clinical follow-up visits should be conducted by the investigator or trial personnel who have been trained to the protocol.

The following information will be collected at each of the time points:

- Any adverse events
- Use and compliance of protocol required antiplatelet medication
- Details of any subsequent coronary interventions (e.g., repeat PCI or CABG)

Note that information obtained through indirect contacts with a subject's healthcare provider or immediate family member will NOT be considered as a trial visit.

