6.5.3 Unscheduled Angiography

There is no required angiographic follow-up for this clinical investigation. However, angiograms for all unscheduled revascularizations must be sent to the Angiographic Core Lab regardless of whether they are target or non-target vessel revascularizations. For all revascularizations performed on both the target lesion (TLR) and the non-target lesion of the target vessel (non-TLR), the angiographic core laboratory will determine the type of revascularization (i.e., TLR, TVR or non-TVR), stent thrombosis, or necessary assessments.

Clinical Investigation Plan

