8.3 Sample Size Calculation and Assumptions

To test the hypothesis specified in Section 8.2.1 for the primary endpoint of TLF at 1-year follow-up, with the following assumptions:

- One-sided alpha: 0.05
- True event rate for the primary endpoint: 10%
- Performance goal: 20%
- Attrition rate: 5%

A sample size of 107 will have approximately 93% statistical power via simulation. To avoid undue influence from a single study site, each site may register at most 20% of the total subjects.

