- Irrespective of the time after the index procedure, any MI that is related to documented acute ischemia in the territory of the implanted stent without angiographic confirmation of stent thrombosis and in the absence of any other obvious cause

- ‡ For studies with ST-elevation MI population, one may consider the exclusion of unexplained death within 30 days as evidence of probable stent thrombosis.

Possible stent thrombosis

Clinical definition of possible stent thrombosis is considered to have occurred with any unexplained death from 30 days after intracoronary stenting until end of trial follow-up.

STROKE

An acute symptomatic episode of neurological dysfunction attributed to a vascular cause lasting more than 24 hours or lasting 24 hours or less with a brain imaging study or autopsy showing new infarction.

- Ischemic Stroke: An acute symptomatic episode of focal cerebral, spinal, or retinal dysfunction caused by an infarction of central nervous system tissue.
- Hemorrhagic Stroke: An acute symptomatic episode of focal or global cerebral or spinal dysfunction caused by a non-traumatic intraparenchymal, intraventricular, or subarachnoid hemorrhage.
- Undetermined Stroke: A stroke with insufficient information to allow categorization as ischemic or hemorrhagic.

Note: an event that last < 24 hours may be adjudicated as a stroke if the following treatments were used:

- Pharmacologic, i.e., thrombolytic drug administration, or

Non-pharmacologic, i.e., neurointerventional procedure (e.g., intracranial angioplasty)

REVASCULARIZATION (Per ARC Circulation 2007; 115: 2344-2351)

Target Lesion Revascularization (TLR)

Clinical Investigation Plan

TLR is defined as any repeat percutaneous intervention of the target lesion or bypass surgery of the target vessel performed for restenosis or other complication of the target lesion. All TLR should be classified prospectively as clinically indicated [CI] or not clinically indicated by the investigator prior to repeat angiography. The target lesion is defined as the treated segment from 5 mm proximal to the stent and to 5 mm distal to the stent.

Target Vessel Revascularization (TVR)

TVR is defined as any repeat percutaneous intervention or surgical bypass of any segment of the target vessel. The target vessel is defined as the entire major coronary vessel proximal and distal to the target lesion which includes upstream and downstream branches and the target lesion itself

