Non Target Lesion Revascularization (Non-TLR)

Any revascularization in the target vessel for a lesion other than the target lesion is considered a non-TLR.

Non Target Vessel Revascularization (Non-TVR)

Revascularization of the vessel identified and treated as the non-target vessel at the time of the index procedure.

Clinically Indicated [CI] Revascularization (TLR/TVR)

A revascularization is considered clinically indicated if angiography at follow-up shows a percent diameter stenosis $\geq 50\%$ and if one of the following occurs:

- A positive history of recurrent angina pectoris, presumably related to the target vessel;
- Objective signs of ischemia at rest (ECG changes) or during exercise test (or equivalent), presumably related to the target vessel;
- Abnormal results of any invasive functional diagnostic test (e.g., Doppler flow velocity reserve, fractional flow reserve);
- A TLR/TVR with a diameter stenosis $\geq 70\%$ in the absence of the above mentioned ischemic signs or symptoms.

TARGET LESION FAILURE (TLF)

TLF is defined as a composite of all cardiac death, myocardial infarction attributed to target vessel or clinically-indicated TLR.

TARGET VESSEL FAILURE (TVF)

TVF is defined as a composite of cardiac death, MI attributed to target vessel, clinically-indicated TLR, or clinically-indicated TVR, non-TLR.

COVID-19 Relatedness Definitions

The COVID-19 relatedness to an adverse event, is adjudicated by the CEC committee into 3 categories: likely related, possibly related, or not likely related, based on the COVID-19 relatedness definitions that are described on the CEC charter. Please refer to the CEC charter for the COVID-19 relatedness definitions.

IN-STENT

Within the margins of the stent.

Clinical Investigation Plan

Minimal Lumen Diameter (MLD)

Minimum lumen diameter is defined as the shortest diameter through the center point of the lumen. Data are collected from two projections.

PERCENT DIAMETER STENOSIS (%DS)

The value calculated as $100 * (1 - \text{MLD}/\text{RVD})$ using the mean values from two orthogonal views (when possible) by QCA.

REFERENCE VESSEL DIAMETER (RVD)

Reference vessel diameter based on QCA is derived from either the user-defined method using average diameter of proximal and distal healthy segments or the interpolated method.

RESTENOSIS

Re-narrowing of the artery following the removal or reduction of a previous narrowing.

TIMI (THROMBOSIS IN MYOCARDIAL INFARCTION) FLOW GRADES

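### Appendix II limits Non-TVR to the vessel treated as non-target at index, so at least 60% of registered subjects cannot have one and some revascularizations fit no defined type

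*Protocol*

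**What the plan says.** The only definition of Non-TVR in either document is in Protocol Appendix II: "Revascularization of the vessel identified and treated as the non-target vessel at the time of the index procedure". The same appendix defines TVR as "any repeat percutaneous intervention or surgical bypass of any segment of the target vessel", TLR as a repeat procedure for the target lesion, and non-TLR as a procedure in the target vessel for another lesion.

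Elsewhere the term appears to cover more:

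- Protocol Section 3.2.2: "The Angiographic Core Lab will determine the type of revascularization (i.e., TLR, TVR or non-TVR"). No other type is listed.
- Protocol Section 4.3, Protocol Appendix X and SAP Section 1.4.3 list All Non-TVR alongside All TVR under Any Revascularization. It is reported in hospital and at 30 days, 180 days, 1 year and 2 years. The SAP adds no definition of its own.
- Protocol Section 6.5.3 requires angiograms for all unscheduled revascularizations to go to the core lab "regardless of whether they are target or non-target vessel revascularizations".

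On who can have a treated non-target vessel, Protocol Section 3.1 (repeated in SAP Section 1.3) says: "A maximum of 40% of subjects with two treated lesions can be registered in the study". Section 5.3.2.2 allows at most one treated non-target lesion, in a different epicardial vessel.

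**The concern.** As written, the definition does not complement TVR. It needs a vessel that was treated as non-target at the index procedure. A subject with only the target lesion treated has no such vessel. A subject with two treated lesions has exactly one, so a later procedure in a third vessel is also left out.

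If the definition is followed, a rate labelled All Non-TVR omits real revascularizations outside the target vessel, and most of the cohort cannot contribute an event. TVR and Non-TVR then need not account for everything in Any Revascularization. A reader would take the rate as covering all other vessels, which it would not do.

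**Working it through.** The documents state no Non-TVR rate, so there is no plan figure to reproduce. The check has two parts: whether the defined types cover all revascularizations, and how many subjects the narrow definition leaves out.

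**Coverage of the types.** Consider a later revascularization by the vessel it occurs in.

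| Vessel revascularized | TLR | TVR | Non-TLR | Non-TVR |
|---|---|---|---|---|
| Target vessel, target lesion | yes | yes | no | no |
| Target vessel, other lesion | no | yes | yes | no |
| Non-target vessel treated at index | no | no | no | yes |
| Any vessel not treated at index | no | no | no | no |

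The last row is the gap. It can occur in any single-lesion subject, and in a two-lesion subject through a third vessel. Nothing visible in either document fills it.

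Section 6.5.3 does not settle the matter. Its reference to target and non-target vessels concerns which angiograms are sent. Its sentence on assigning types begins "For all revascularizations performed on both the target lesion (TLR) and the non-target lesion of the target vessel (non-TLR"), so it covers only target-vessel procedures, yet it lists non-TVR among the possible results.

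**Share of subjects who cannot have a Non-TVR as defined.** Inputs: N up to 107 (Protocol Section 5.6) and at most 40% with two treated lesions (Protocol Section 3.1).

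- Most two-lesion subjects allowed: 0.40 × 107 = 42.8, so 42.
- Fewest single-lesion subjects: 107 − 42 = 65.
- Share: 65 / 107 = 60.7%.
- For any N up to 107 the floor is 100% − 40% = 60%, reached exactly when N is a multiple of 5.

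Under a definition covering every vessel other than the target vessel, all 107 could have an event.

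**Effect per missed subject.** For each subject whose only revascularization outside the target vessel falls outside the definition:

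- Denominator 107: 1 / 107 = 0.93 percentage points.
- Denominator after the planned 5% attrition (Protocol Section 8.3): 107 × 0.95 = 101.65, so 101 whole subjects; 1 / 101 = 0.99 percentage points.

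The 5% is the sample-size assumption for the 1-year primary endpoint. It is used here only to indicate scale.

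**Total understatement.** This is the number of such subjects times the step above. The documents give no rate of revascularization outside the target vessel, so it cannot be computed.

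**The case against.** The strongest reply has four parts.

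1. **The label.** In the endpoint list All TVR sits above ID-TVR and All TLR above ID-TLR, so All may mean regardless of ischemic indication rather than every vessel. That is a fair reading, and the label alone does not prove a contradiction. It does not close the gap, because Non-TVR still stands beside TVR under Any Revascularization and as one of only three core-lab types.

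2. **Intent.** The sponsor may have meant to follow only the vessel treated at index, in which case the reported rate is correct by its own definition. The documents do not say so, and General Exclusion Criterion 10 applies the term non-target vessel to PCI before consent, hence before any index treatment. If the narrow scope is intended, the label and denominator do not convey it.

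3. **Unseen rules.** The CEC charter and core-lab guidelines are not in the documents and may use a broader rule. The understatement is therefore conditional. However, Protocol Section 10.9.4 binds the CEC to the protocol's definitions as well as to its charter, so a broader working rule would differ from the protocol text.

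4. **Importance.** The endpoint is descriptive, and SAP Section 2.11 confines formal testing to the primary endpoint. On plain wording the missed events still count in Any Revascularization and in DMR. At event level, Any Revascularization less All TVR would show what the narrow line omits. All of this stands. It limits the point to one untested line. Nor is the 60% an error in a result: it is the share of subjects outside the definition.

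**Conclusion.** The concern holds, as an optional correction. The Appendix II definition leaves a class of revascularization with no type, and at least 60% of registered subjects (65 of 107 at full enrolment) cannot have a Non-TVR as defined. If the text is followed and such events occur, the descriptive All Non-TVR rate is understated by 0.93 to 0.99 percentage points per affected subject on the denominators shown. The total is unknown.

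This rests on three conditions: the 40% cap is respected; the definition is read in its ordinary sense, as requiring treatment at index; and no unseen core-lab or CEC rule overrides it. The 60% floor applies to registered subjects. The reported denominators are the FAS and PP sets, whose definitions are not visible.

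Primary TLF, its test and its power do not use Non-TVR. Any Revascularization and DMR would be affected only if they were built by adding TVR and Non-TVR, which the documents do not say. Confidence is high on the wording, and lower on whether any reported rate will in fact be wrong.

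**What to change.** In Appendix II, define Non-TVR as *any revascularization of a coronary vessel other than the target vessel, whether or not that vessel was treated at the index procedure*. Events in a non-target vessel treated at index can be reported as a subset. Align the core-lab and CEC instructions, and the sentence in Section 6.5.3 that assigns types, with this definition.

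If the sponsor does intend the narrow endpoint, the alternative is to relabel it and give its denominator as two-lesion subjects. A type would still be needed for the remaining procedures.

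The cost is one sentence in Appendix II, a small edit to Section 6.5.3, and a check of the core-lab guidelines and CEC charter, whose content is not visible here. No new data are needed: Section 6.5.3 already sends angiograms for all unscheduled revascularizations to the core lab, and Section 6.5.1 collects at each visit "Details of any subsequent coronary interventions (e.g., repeat PCI or CABG"). The foreseeable downside is a possibly higher reported Non-TVR rate.

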19.0 APPENDIX III: SITE CONTACT INFORMATION

Contact information for each participating clinical site is available under separate cover by contacting the Sponsor.

Clinical Investigation Plan

20.0 APPENDIX IV: RISK FOR THE STUDY AND RATES OF FORSEEABLE ADVERSE EVENTS

There are risks, discomforts, and inconveniences to a subject, associated with any research (or to an embryo, unborn child or nursing infant if a subject become pregnant). These risks deserve careful thought.

While in the study, the risks and adverse effects of each are listed, but they will vary from person to person. A subject should talk with the Study Doctor if he/she has any questions. There may be some discomforts or inconveniences associated with the study tests and procedures.

Electrocardiogram

The ECG test is a recording of the electrical activity of your heart and an ECG is harmless. The ECG will be performed based on the standard of care of the hospital. The sticky pads (electrodes) that are placed on a subject's chest can sometimes cause discomfort such as redness or itching. A subject's chest may need to be shaved before attaching these pads. Irritation from shaving also may occur.

Blood Sample

The risk of inserting a needle into a vein in your arm may include temporary discomfort from the needle stick. There is also a small risk of infection, bruising, swelling, bleeding or fainting. These risks are minimized by cleansing the site carefully prior to obtaining the blood sample and applying pressure to the site after the blood sample is obtained.

Imaging Catheter, PCI, and Contrast Media

Below are the possible risks that may occur with use of ABT NG DES 48. These risks are not specific to the ABT NG DES 48 and may happen with any stent for heart vessels:

- Allergic reactions or hypersensitivity to rubber, contrast agent, anesthesia, device materials (cobalt, chromium, tungsten, nickel, methacrylic polymer, and fluoropolymer), and everolimus, anticoagulation, or antiplatelet drugs

Clinical Investigation Plan

- Vascular complications in arteries used to access the coronary artery which may require blood transfusion or surgical artery repair, including:
 - Complications at the groin or arm access site
 - Bleeding
 - Formation of an abnormal connection between an artery and the vein next to it
 - Leaking of blood from an artery to the surrounding tissue (usually as a result of a puncture to the artery)
 - Weakness in wall of artery (causing possible serious bleeding complications)
 - Partial or complete tear of the wall of the artery
 - Vessel puncture or rupture
 - Movement of air, tissue, plaque, blood clot, or device material (stent or catheter parts) downstream in the arteries resulting in blockage in blood flow
 - Nerve damage caused by compression of the nerves, injury to the nerve, or interruption of blood supply to the nerves
 - Decreased blood supply to the arms and / or legs which may cause cramping or pain
- Complications at the heart arteries which may require additional treatment or surgery, including:
 - Complete blockage of the coronary artery, which may require a repeat procedure or emergency surgery to reopen the coronary artery
 - Formation of an abnormal connection between a heart artery and the vein next to it
 - Leaking of blood from a heart artery to the surrounding tissue (usually as a result of a puncture to the artery)
 - Weakness in wall of the heart artery (causing possible serious bleeding complications)
 - Partial or complete tear of the wall of the artery supplying the heart muscle
 - Puncture or rupture of the wall of the artery supplying the heart muscle
 - Movement of air, tissue, plaque, blood clot, or device material (stent or catheter parts) that partially or completely blocks the heart artery and / or implanted stent
 - Development of blood clots partially or completely blocking blood flow within the artery and / or the implanted stent
 - Narrowing or re-narrowing of the treated heart artery
- Complications in the sac around the heart which may require additional treatment, including:

Clinical Investigation Plan

- Rapid accumulation of blood in the sac around the heart resulting in compression of the heart so it cannot pump out blood to the rest of the body which may require additional treatment or emergency surgery
- An abnormal accumulation of blood around the heart
- Inflammation of the tissue around the heart (causing possible chest pain)
- Irregular heartbeats (caused by abnormal electrical activity in the heart from the upper or lower heart chambers)
- Decreased blood and / or oxygen supply to part of the heart muscle which may cause:
 - Heart attack (permanent damage of an area of the heart tissue, due to interruption in the blood flow to the heart muscle)
 - Temporary spasm of the heart arteries
 - Chest pain (which may radiate to jaw or arm) or discomfort caused by inadequate supply of blood to the heart)
- Stroke or temporary stroke symptoms as a result of decreased oxygen to the brain causing blurred vision, dizziness, faintness, and numbness
- Abnormal organ function in very ill patients including:
 - Stoppage of the heart
 - Heart function failure (potentially leading to the development of fluid in the lungs and severe breathing difficulty)
 - Lung function failure (potentially leading to severe breathing difficulty)
 - Kidney failure
 - Shock (a life-threatening condition in which blood pressure is too low to maintain adequate-blood flow to your organs)
- Blood count abnormalities
- Low or high blood pressure
- Infection
- Nausea and vomiting
- Feeling of the heart beating rapidly (palpitations), dizziness, or fainting
- Chest pain
- Fever
- Pain

Clinical Investigation Plan

- Death

Magnetic resonance imaging (MRI): If a subject requires a magnetic resonance imaging (MRI) scan, tell the doctor or MRI technician that the subject has a stent implant. Test results indicate that the stents of the ABT NG DES 48 are MR conditional. Subjects with single or overlapped XIENCE stents can undergo MRI scans safely under the following conditions:

- Static magnetic field of 1.5 and 3 Tesla
- Maximum spatial field gradient of 3000 gauss/cm (30 T/m)
- Maximum MR system reported whole-body-averaged Specific Absorption Rate (SAR) of 2.0 W/kg for each duration of a sequence
- Normal operating mode if the MR system for both gradients and SAR
- Maximum gradient slew rate capability of 200 T/m/s

The stent(s) should not migrate in this MRI environment, and MRI may be performed immediately following the implantation of the stent of ABT NG DES 48. Prior to undergoing an MRI scan, inform the doctor that the subject has a stent of ABT NG DES 48.

There may be other risks or discomforts to a subject that are not known at this time. If important information is learned during the course of this clinical investigation, the site will be notified by the Sponsor. The Study Doctor from the site will discuss with a subject important new information that is learned during the course of this study that may affect a subject's condition or willingness to continue to take part in this clinical investigation.

If a subject is a woman who is able to become pregnant, it is expected that the subject will use an effective method of birth control to prevent exposing a fetus to a potentially dangerous agent with unknown risk. If a subject is pregnant or currently breast feeding, she should not participate in this study.

The rates of foreseeable adverse events are:

Anticipated Adverse Events	Frequency Rate Ranges
----------------------------	-----------------------

Clinical Investigation Plan

Category	Subcategory	Very common: ≥10%	Common: ≥ 1.0% to < 10%	Uncommon : ≥ 0.1% to < 1.0%	Rare: ≥ 0.01% to < 0.1%	Very Rare: < 0.01%	
	Allergic reaction or hypersensitivity to latex, contrast agent anesthesia, device materials, and drug reactions to everolimus, anticoagulation, or antiplatelet drugs.		X				
Vascular access complications which may require transfusion or vessel repair, including:	Catheter site reactions		X				
	Bleeding (ecchymosis, oozing, hematoma, hemorrhage, retroperitoneal hemorrhage)			X			
	Arteriovenous fistula, pseudoaneurysm, aneurysm, dissection, perforation / rupture	Arteriovenous fistula					X
		aneurysm			X		
		dissection		X			
		Perforation/rupture		X – for CTO patients only	X		
	Embolism (air, tissue, plaque, thrombotic material or device)	air/ fat embolism					X
		Arterial, aortic, peripheral embolism			X		
	Peripheral nerve injury			X			
	Peripheral ischemia					X	
Coronary artery complications which may require additional intervention, including:	Total occlusion or abrupt closure			X			
	Arteriovenous fistula, pseudoaneurysm, aneurysm, dissection, perforation / rupture	Arteriovenous fistula			X		
		pseudoaneurysm			X		

Clinical Investigation Plan

		aneurysm			X		
		dissection		X			
		Perforation/rupture		X – for CTO patients only	X		
	Tissue prolapse/plaque shift				X		
	Embolism (air, tissue, plaque, thrombotic material, or device)				X		
	Coronary or stent thrombosis (acute, subacute, late, very late)	Thrombosis in device		X – for CTO patients only	X		
		Coronary artery thrombosis, stent thrombosis (cumulative definite/ probable, 1 year data)			X		
	Stenosis or restenosis			X			
Pericardial complications which may require additional intervention, including:	Cardiac tamponade						X
	Pericardial effusion				X		
	Pericarditis						X
Cardiac arrhythmias (including conduction disorders, atrial and ventricular arrhythmias)	Aspecific				X		
	conduction disorders				X		
	Atrial arrhythmias	Atrial fibrillation		X			

Clinical Investigation Plan

		Atrial flutter			X		
		Atrial tachycardia			X		
	ventricular arrhythmias	Ventricular fibrillation					X
		Ventricular tachycardia			X		
Cardiac ischemic conditions (including myocardial ischemia, myocardial infarction (including acute), coronary artery spasm, and unstable or stable angina pectoris)	Myocardial Ischemia				X		
	Myocardial Infarction			X			
	Coronary Artery Spasm						X
	unstable or stable angina pectoris			X			
Stroke/Cerebrovascular accident (CVA) and Transient Ischemic Attack (TIA)	Stroke/CVA	Intracranial hemorrhage					
		Thrombotic, ischemic		X			
	TIA				X		
System organ failures	Cardio-respiratory arrest				X		
	Cardiac failure	Cardiac failure Ventricular failure			X		X

Clinical Investigation Plan

	Cardiopulmonary failure (including pulmonary edema)	Acute / chronic respiratory failure		X		
		respiratory distress			X	
		dyspnea			X	
		pulmonary edema			X	
	Renal insufficiency / failure			X		
	Shock				X	
Blood cell disorders (including Heparin Induced Thrombocytopenia (HIT))				X		
Hypotension					X	
hypertension				X		
Infection				X		
						X
					X	
					X	
Nausea and vomiting					X	
Palpitations, dizziness, and syncope	Palpitations				X	
	Dizziness				X	
	Syncope			X		
Chest pain				X		

Clinical Investigation Plan

Fever			X		
Pain			X		
Death		X			

Clinical Investigation Plan

